7.0 DATA SUBMISSION SCHEDULE

Case Report Form	Submission Schedule
Original Consent Form	Prior to registration
Eligibility Checklist Demographics Clinical Characteristics Medical/Surgical History Form	Prior to starting treatment. Data collection will be captured in RedCap.
Intra-operative Findings Operative and Post-procedural Form	Following receipt of operative report Following receipt of discharge summary Data collection will be captured in RedCap.
Adverse Event Assessment	At the time of any unanticipated and related event
Follow-Up Form: First and Second postop visit	Approximately 30 and 90 days following surgery following routine clinic visit for post-surgical evaluation Data collection will be captured in RedCap.

8.0 DATA AND SAFETY MONITORING

In compliance with the Washington University Institutional Data and Safety Monitoring Plan, the Principal Investigator will provide a Data and Safety Monitoring (DSM) report to the Washington University Quality Assurance and Safety Monitoring Committee (QASMC) and to Olympus, the study sponsor, semi-annually beginning six months after accrual has opened (if at least five patients have been enrolled) or one year after accrual has opened (if fewer than five patients have been enrolled at the six-month mark).

The Principal Investigator will review all patient data at least monthly and provide an annual report to the Quality Assurance and Safety Monitoring (QASM) Committee. This report will include:

- HRPO protocol number, protocol title, Principal Investigator name, data coordinator name, regulatory coordinator name, and statistician

- Date of initial HRPO approval, date of most recent consent HRPO approval/revision, date of HRPO expiration, date of most recent QA audit, study status, and phase of study
- History of study including summary of substantive amendments; summary of accrual suspensions including start/stop dates and reason; and summary of protocol exceptions, error, or breach of confidentiality including start/stop dates and reason
- Study-wide target accrual and study-wide actual accrual
- Protocol activation date
- Average rate of accrual observed in year 1, year 2, and subsequent years
- Expected accrual end date
- Objectives of protocol with supporting data and list the number of participants who have met each objective
- Measures of efficacy
- Early stopping rules with supporting data and list the number of participants who have met the early stopping rules
- Summary of toxicities
- Abstract submissions/publications
- Summary of any recent literature that may affect the safety or ethics of the study

The study principal investigator and Research Patient Coordinator will monitor for serious adverse events on an ongoing basis. Once the principal investigator or Research Patient Coordinator becomes aware of a research related adverse event, the AE will be reported to the HRPO according to institutional guidelines and to Olympus, the study sponsor.

9.0 STATISTICAL CONSIDERATIONS

9.1 Study Objectives and Endpoints

The primary objective of the study is to determine if the use of the Thunderbeat™ device provides a reduction in operative blood loss. The measurement of operative blood loss will come from the intraoperative anesthesia notes where estimated blood loss is recorded during each surgical procedure.

The secondary objectives are intraoperative and postoperative morbidity, hospital length of stay and operative time.

Primary endpoint

The primary endpoint will be the estimated operative blood loss. The estimated blood loss will be measured per the standard of care and will be documented in the operation log.

Secondary endpoints

- Operation time measured from the beginning of the surgical procedure (incision of the skin) to the end of the surgical procedure (closure of the skin).
- Anesthesia time measured from the initiation of anesthesia induction to the time of extubation
- Perioperative complications:
 - Iatrogenic injury
 - Need for conversion from laparoscopic approach to open procedure
 - Need for the use of other hemostatic devices or therapies
 - Intraoperative requirement of blood product transfusion
- Postoperative complications through 90 days from day of surgery:
 - Secondary bleeding/hematoma
 - Wound infection
 - Gastroparesis
 - Postoperative pancreatic fistula
 - Intraabdominal abscess

- Anastomotic leakage
- Re-intervention (operational)
- Postop requirement for blood product transfusion
- Hospital mortality
- Overall cost of the operation, calculated by the indirect and direct costs during the hospital stay and the costs accumulated 90 days postoperatively

9.2 Study Design

To achieve comparable groups for known and unknown risk factors randomization will be performed as unistratified block randomization with random block sizes in a 1:1 allocation ratio. Allocation to treatment will be carried out by means of a computer-generated random study numbers with group assignment.

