3.0 PATIENTSELECTION

3.1 Inclusion Criteria

1. Scheduled to undergo an elective open or laparoscopic Whipple procedure
2. At least 18 years of age.
3. Karnofsky performance status \geq 80% (see Appendix A).
4. Able to understand and willing to sign a written informed consent document.

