9.4 Data Analysis

Data analysis for this study will be descriptive in nature. Demographic and clinical characteristics of the sample, as well as intraoperative findings and post-surgery complications will be summarized using descriptive statistics. The incidences of surgical complications and procedure-related adverse events will be calculated, and the confidence intervals will also be provided.

Patients assigned to the Thunderbeat™ group will be compared with those who had conventional techniques using χ^2 tests for categorical variables and Student's t-tests for continuous variables. For the t-tests equal variances were not be assumed, unless significant by Levene's test. Mann-Whitney *U* tests will be utilized for non-normally distributed variables. Two-tailed *P* values 0.05 will be considered statistically significant.

Multivariate analyses for intraoperative blood loss (mL), operative time (minutes), postoperative morbidity (any grades 1–5 and major grades 3–5), and hospital length of stay (days) will be performed using binary logistic regression and linear regression models to examine the relationship between intervention groups and examined outcomes and to identify potential confounders. The results of multivariate analyses will be expressed as odds ratios with corresponding 95% confidence intervals. All analyses will be performed using SPSS 20.0 statistical software (SPSS Inc.Chicago, IL).

REFERENCES

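### Open and laparoscopic cases are mixed, but planned approach is neither a named stratification factor nor a pre-specified covariate, and linear-model results are to be given as odds ratios

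*Combined protocol and SAP*

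**What the plan says.** All references are to the combined protocol and SAP.

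- **Section 3.1** makes a patient eligible if "Scheduled to undergo an elective open or laparoscopic Whipple procedure". Section 9.1 lists "Need for conversion from laparoscopic approach to open procedure" among the secondary endpoints, so laparoscopic starts are expected.
- **Section 9.2** states that "randomization will be performed as unistratified block randomization with random block sizes in a 1:1 allocation ratio". No stratification factor is named there or in Section 5.2.
- **Section 9.4** says that Thunderbeat patients "will be compared with those who had conventional techniques using" chi-squared tests and t-tests, and that Mann-Whitney "tests will be utilized for non-normally distributed variables". These comparisons are unadjusted.
- **Section 9.4** also plans multivariate models for blood loss (mL), operative time (minutes), morbidity and length of stay (days). They are logistic and "linear regression models to examine the relationship between intervention groups and examined outcomes and to identify potential confounders". No covariate is listed.
- **Section 9.4** then says: "The results of multivariate analyses will be expressed as odds ratios with corresponding 95% confidence intervals".
- **Section 7.0** lists pre-treatment forms ("Eligibility Checklist Demographics Clinical Characteristics Medical/Surgical History Form") without their fields, so planned approach may or may not be captured.

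**The concern.** If approach affects blood loss, its variance stays in the error term of the unadjusted test. With 30 patients per arm, a chance imbalance in approach can also move the estimate in either direction. The plan would then have no pre-specified adjusted estimate to set beside it. Approach could still enter the regressions, but as a choice made after seeing the data.

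A second problem does not depend on how many cases are laparoscopic. A linear model of mL, minutes or days gives a mean difference, not an odds ratio. As written, the plan therefore does not define an effect measure for an adjusted analysis of its primary endpoint.

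**Working it through.** **Inputs from the documents.** 60 patients, 30 per arm; 20% reduction in blood loss; alpha 0.05; power above 80% (Section 9.3); two-tailed tests (Section 9.4).

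**Assumed, because the documents do not give them.** Lognormal blood loss; log SD within approach 0.3, 0.5 or 0.8; laparoscopic/open ratio of blood loss 0.8, 0.7, 0.6 or 1.0; number laparoscopic L = 20 or 6 of 60.

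**1. The plan's own figure.** N = 60 cannot be reproduced, since no SD, CV or control mean is stated. It can be inverted. For 80% power on the log scale, the log SD must be at most |ln 0.8| × √(30/2) / (1.960 + 0.842) = 0.2231 × 3.873 / 2.802 ≈ 0.31. On the raw scale, the CV must be at most 0.20 × 3.873 / 2.802 ≈ 0.276. So log SD 0.3 is close to what the stated power requires. At 0.5 and 0.8, power is far below 80% with or without adjustment.

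**2. Hand check of the precision loss.** Ignoring approach inflates the standard error by √(1 + p(1−p)d²), where p is the laparoscopic share and d is the approach difference in within-approach SDs. Take p = 1/3, ratio 0.7 and log SD 0.3.
- d = 0.3567/0.3 = 1.19, and the inflation is √(1 + 0.222 × 1.41) = 1.146.
- Adjusted: z = 0.2231 × 3.873/0.3 = 2.88, and power = Φ(2.88 − 1.96) ≈ 82%.
- Unadjusted: z = 2.88/1.146 = 2.51, and power = Φ(2.51 − 1.96) ≈ 71%.

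The loss is about 11 points.

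**3. Simulated power (%), unadjusted → adjusted, for ratios 0.8 / 0.7 / 0.6.** At least 40,000 trials per cell, so simulation error is at most about √(0.25/40,000) = 0.25 points.

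| log SD | L | t-test → regression on mL with approach | Mann-Whitney → van Elteren |
|---|---|---|---|
| 0.3 | 20 | 74→78, 68→77, 60→77 | 74→77, 67→77, 56→77 |
| 0.3 | 6 | 77→78, 75→78, 72→78 | gain about 0 to 8 points |
| 0.5 | 20 | 34.4→35.2, 32.9→35.0, 30.3→34.4 | 36.7→36.8, 34.5→36.8, 31.8→37.0 |
| 0.5 | 6 | 35.6→35.7, 35.0→35.7, 33.7→35.1 | 37.3→37.0, 36.8→37.1, 35.5→37.0 |
| 0.8 | 20 | 14.2→14.5, 13.9→14.3, 13.6→14.2 | 17.5→17.5, 17.3→17.2, 16.7→17.4 |

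Before rounding, the gains in the first row run from about 4 to 21 points.

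**4. If approach has no effect (ratio 1.0).** With L = 20 and log SD 0.5, regression goes from 35.9 to 35.6% and the rank test from 38.1 to 37.0%. Over the settings tried, the loss is about 0.3 to 1.5 points.

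**5. Type I error.** With L = 20 and log SD 0.5, it is 4.6 to 4.8% for the t-test, 4.7 to 4.9% for regression, and 4.9 to 5.0% for both rank tests.

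**6. Chance imbalance.** The number laparoscopic in one arm is hypergeometric (60, L, 30). With L = 20 the mean absolute difference between arms is 2.9 cases, and P(difference ≥ 6) = 0.170, half in each direction. With L = 6 that probability is 0.024. The shift in the mL estimate, as a share of the arm mean, is (difference/30)(1 − ratio) / (1 − (1 − ratio)L/60). For L = 20 and a difference of 6, this is 0.2 × 0.2/0.933 = 4.3%, 0.2 × 0.3/0.9 = 6.7%, and 0.2 × 0.4/0.867 = 9.2%.

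**7. Regression or rank test.** With L = 20 and ratio 0.8, mL regression with approach has less power than even the unadjusted Mann-Whitney test: 35.2 against 36.7% at log SD 0.5, and 14.5 against 17.5% at 0.8. Under skew, the choice of method matters as well as the covariate.

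**The case against.** The strongest reply is that unstratified blocked randomisation with an unadjusted test is valid. That is correct. A reader might infer that mixing the approaches biases the comparison or inflates false positives. The documents do not support this: allocation is randomised, chance imbalance favours either arm equally often, and type I error stays near 5%.

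It can also be said that nothing in the documents shows that approach affects blood loss, or that many cases will be laparoscopic. This stands, and it is why no single size can be claimed.

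A reader might infer that adjustment is absent. It is not: Section 9.4 already plans a multivariate analysis of blood loss by group. What is missing is a named covariate and a suitable effect measure. Section 9.4 also does not assign logistic and linear models to outcomes. A logistic model of blood loss would need a cut-point, however, and none is given.

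*Unistratified* may be a slip for unstratified, or may mean one unnamed factor. If that factor is approach, the stratification half of the point falls away; the covariate and odds-ratio parts remain.

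The standardised technique and surgeon experience required by Section 5.2 neither fix the approach nor balance it. Section 9.4 calls the analysis descriptive, but it also sets a significance threshold, and Section 9.3 claims power.

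**Conclusion.** The point holds as an inexpensive improvement worth considering, together with one reporting rule that is wrong as written. Planned approach is neither a named stratification factor nor a pre-specified covariate, and odds ratios cannot come from linear models of mL, minutes or days.

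The precision cost could be anything from nil to substantial. Under the assumptions above, adjustment changes power as follows:

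- log SD 0.3: about +4 to +21 points with 20 laparoscopic cases, and about 0 to +8 with 6;
- log SD 0.5: about 0 to +5 points;
- log SD 0.8: within about 1 point of zero;
- approach irrelevant: about 0.3 to 1.5 points lost.

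It would be tempting to call the cost either modest or large. Neither is supported, because share, approach effect and SD are all assumed. The larger gains arise where variability is low enough for the plan's own power claim. The missing SD behind N = 60 is a separate and larger question.

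**What to change.** 1. Confirm that planned approach (open or laparoscopic) is recorded before randomisation. Use planned rather than final approach in every analysis, because conversion happens after randomisation.
2. In Section 9.4, pre-specify planned approach as a fixed covariate, with treatment, in the linear regressions of blood loss and operative time. Report adjusted mean differences with 95% CIs. Keep odds ratios for the logistic models only; length of stay, if modelled linearly, also needs a mean difference.
3. Name one primary analysis of blood loss in advance: either the approach-adjusted regression or, if skew is expected, a rank test stratified by planned approach (van Elteren). Make the other, and the unadjusted test, supporting analyses. The main estimate and the P value should not come from different methods without a stated rule.

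Optional: clarify *unistratified*; stratify the block list by planned approach if enrolment has not begun, at the price of a possible incomplete block in each stratum; and name surgeon as a covariate in advance or leave it out.

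**Cost.** One model term, one degree of freedom and, if not already captured, one pre-randomisation field. The stratified rank test may need a short script. If approach is irrelevant, about 0.3 to 1.5 points of power are lost. The gain is small if few cases are laparoscopic or blood loss is very variable. Sample size and clinical care are unchanged.

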9.3 Sample Size

Appropriate sample size is calculated based on assumption of difference of 20 percent in blood loss in favor of the Thunderbeat™ device as compared with conventional techniques. This difference is considered clinically relevant based on previous similar studies [9-11]. A sample size of 60 is considered sufficient to prove this difference, if present (alpha error set at 0.05, power>80 percent).

Approximately 100 patients per year undergo a Whipple procedure at Washington University Medical Center. The estimated time frame to enroll 60 patients is approximately 18 to 24 months.

The total expected enrollment is 60 patients: 30 Thunderbeat and 30 conventional.

9.4 Data Analysis

Data analysis for this study will be descriptive in nature. Demographic and clinical characteristics of the sample, as well as intraoperative findings and post-surgery complications will be summarized using descriptive statistics. The incidences of surgical complications and procedure-related adverse events will be calculated, and the confidence intervals will also be provided.

Patients assigned to the Thunderbeat™ group will be compared with those who had conventional techniques using χ^2 tests for categorical variables and Student's t-tests for continuous variables. For the t-tests equal variances were not be assumed, unless significant by Levene's test. Mann-Whitney *U* tests will be utilized for non-normally distributed variables. Two-tailed *P* values 0.05 will be considered statistically significant.

Multivariate analyses for intraoperative blood loss (mL), operative time (minutes), postoperative morbidity (any grades 1–5 and major grades 3–5), and hospital length of stay (days) will be performed using binary logistic regression and linear regression models to examine the relationship between intervention groups and examined outcomes and to identify potential confounders. The results of multivariate analyses will be expressed as odds ratios with corresponding 95% confidence intervals. All analyses will be performed using SPSS 20.0 statistical software (SPSS Inc.Chicago, IL).

REFERENCES

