2.0 OBJECTIVES

2.1 Primary Objective

This is a prospective observational feasibility/QI registry trial to evaluate operative blood loss and post-operative morbidity following use of the Thunderbeat™ device during the Whipple procedure. This will be compared to patients whose Whipple procedure will be performed using conventional dissection and hemostasis techniques.

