3.2 Exclusion Criteria

1. Pregnant or breastfeeding.
2. Surgeon's opinion at the time of dissection that the subject's well being (e.g. bleeding or other independent acute health problems) would be compromised.

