5.2 Randomization

Sixty patients will be recruited according to the sample size calculation. Randomization will be performed by a Research Patient Coordinator and the patient assigned to the Thunderbeat™ group or the conventional group in a 1:1 ratio. Randomization will only occur after the patient has signed the informed consent and will be documented in the case report file as well as communicated to the treating surgeon.

Thunderbeat™ group (n=30)

In the Thunderbeat™ group, dissection and hemostasis of vessels will be performed using the Thunderbeat™ device (Olympus, Japan).

Control group (n=30)

In the conventional group, scissors, ligatures, clips and sutures will be used for dissection and hemostasis as necessary.

Minimizing treatment bias

A standardized operation technique will be used in both groups. The same Thunderbeat™ device will be used throughout the length of the study. The participating surgeons will have had experience performing at least 100 Whipple procedures to guarantee comparable treatment of patients.

Minimizing measurement bias

The patients will be blinded to the assigned operating technique. Surgeon's blinding will not be possible due to the different techniques used during the operation.

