5.3 Operative Procedure

The surgical procedure will be conducted as planned. The surgeon will follow the subject's assigned group assignment (Thunderbeat™ or conventional) unless determined to be potentially

detrimental to the optimal care of the patient. At that point, all techniques for dissection and hemostasis may be utilized as the surgeon deems necessary.

At least 5 of the procedures will be videotaped for future use to produce educational and training materials. No identifying information will be contained in the video.

The measurement of estimated blood loss (EBL) will come from the intraoperative anesthesia notes where (EBL) is recorded during each surgical procedure in Allscripts and Clindesk. The estimate of operative blood loss is measured by volume in the suction canisters and pads and is historically documented by the operative nursing staff during the operation.

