5.6 Criteria for Removal from Study

If at any time the constraints of this protocol are considered to be detrimental to the patient's health (e.g. bleeding or other acute health problem) and/or the patient no longer wishes to proceed with the protocol intervention, the patient should be removed from the study and the reason(s) for discontinuation documented in the case report forms.

Otherwise, the patient will receive the intervention and be followed as described.

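### Section 9.4 defines one comparison group by assignment and the other by technique received, and nothing says that patients switched or removed during surgery are analysed as randomized

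*Combined protocol and SAP*

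**What the plan says.** Section 9.4 gives the only rule for who is compared with whom in the group tests: "Patients assigned to the Thunderbeat™ group will be compared with those who had conventional techniques". The regression paragraph that follows speaks only of intervention groups, without saying whether these are assigned or received. Sections 2.1 and 2.2 also describe the comparator by technique: "This will be compared to patients whose Whipple procedure will be performed using conventional dissection and hemostasis techniques".

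Section 5.2 randomizes 1:1, 30 per arm, and describes control treatment thus: "In the conventional group, scissors, ligatures, clips and sutures will be used for dissection and hemostasis as necessary". It notes that the surgeon cannot be blinded.

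Three provisions can separate assignment from what happens in theatre:

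- Section 5.3 applies to both arms: "The surgeon will follow the subject's assigned group assignment (Thunderbeat™ or conventional) unless determined to be potentially" harmful to the patient's care. It continues: "At that point, all techniques for dissection and hemostasis may be utilized as the surgeon deems necessary".
- Section 5.6 covers patients for whom the protocol's constraints are judged harmful, with bleeding as an example, and those who no longer wish to proceed: "the patient should be removed from the study and the reason(s) for discontinuation documented in the case report forms".
- The second exclusion criterion in 3.2 turns on "Surgeon's opinion at the time of dissection that the subject's well being" would be compromised, again with bleeding as an example.

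None of these says how such patients are analysed. The documents define no intention-to-treat, as-treated or per-protocol population.

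**The concern.** The words *assigned* and *had* pick out the same patients only if every operation is completed with the assigned technique. Section 5.3 allows for operations that are not. For those patients the sentence in 9.4 has more than one meaning:

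- A control finished with an energy device could be counted as a control, or left out as not having had conventional technique.
- A Thunderbeat patient finished with clips and sutures is in the device group by assignment, but has also had conventional techniques and could be placed on both sides.

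Two analysts could therefore build different datasets from the same sentence, and the choice could be made after blood loss is known.

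The event that creates the ambiguity occurs after randomization and is decided by a surgeon who knows the arm. It is probably related to blood loss, the primary endpoint. Grouping patients on such an event gives up the comparability that 9.2 randomizes to achieve, for blood loss and also for operative time, transfusion and cost.

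**Working it through.** **The plan's own figure.** Section 9.3 gives 60 patients for a 20% reduction, alpha 0.05 and power above 80%, but no mean or SD, so 60 can be neither reproduced nor refuted. It can be inverted for the coefficient of variation (CV) that it implies. With the two-sided test of 9.4 and the normal approximation, n per arm = 2(z₀.₉₇₅ + z₀.₈₀)² CV² / 0.20². Setting n = 30:

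CV = 0.20 / [(1.960 + 0.842) × √(2/30)] = 0.20 / (2.802 × 0.2582) = 0.276.

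This is the largest CV at which 60 patients give 80% power.

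**Inputs for the illustration.** From the documents: 30 per arm and a true ratio of 0.80. Assumed, because the documents are silent: log-normal loss with equal CV in both arms, CV from 0.28 to 1.0, and one or three of 30 controls dropped. Each scenario uses 20,000 simulated trials.

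**Formula.** Ratio after loss = Thunderbeat mean / mean of the controls who remain. For example, at CV 0.2765, dropping the three highest controls lowers the control mean from 1.00 to 0.942, and 0.80 / 0.942 = 0.85.

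| Controls lost of 30 (true ratio 0.80) | CV 0.28 | CV 0.5 | CV 0.75 | CV 1.0 |
|---|---|---|---|---|
| One, at random from the top third | 0.81 | 0.82 | 0.82 | 0.83 |
| The single highest | 0.82 | 0.84 | 0.87 | 0.90 |
| Three, at random from the top third | 0.83 | 0.85 | 0.88 | 0.89 |
| The three highest (worst case) | 0.85 | 0.90 | 0.97 | 1.05 |
| The three highest, ratio of medians | 0.83 | 0.85 | 0.87 | 0.89 |

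**With no true effect.** Dropping the three highest controls makes the device look 6% worse at CV 0.28 and 13% to 31% worse at CV 0.5 to 1.0. Two-sided type I error rises from about 5% to about 16% at CV 0.28 and 18% to 19% at CV 0.5 to 1.0. The excess is in the direction against the device: at CV 0.28, significant results in its favour fall from 2.3% to 0.4%.

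**Loss unrelated to bleeding.** The estimate stays unbiased. At CV 0.2765, losing three controls at random lowers power only from 80.0% to 77.8%. The harm therefore comes from selection on the outcome, not from the smaller number.

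**As randomized.** The comparison stays 30 against 30, and the sample size is unaffected.

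**The case against.** The strongest reply is that the sentence in 9.4 is loosely worded and simply names the two arms. Section 5.2 sets the conventional group by assignment. A control started with ligatures and finished with a device has still had conventional techniques; to exclude that patient one must read *only* into the sentence, and the word is not there. Section 9.1 lists "Need for the use of other hemostatic devices or therapies" as a secondary endpoint, which can be compared between arms only if such patients stay in them. The wording in 2.1 and 2.2 describes planned treatment and does not define an analysis population.

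Much of this stands. A reader might infer that the plan drops switched controls and so breaks the randomized comparison. No sentence does so, and the 9.1 endpoint points the other way. What the reply does not supply is a statement that patients are analysed as randomized, and it leaves the two definitions in 9.4 unreconciled.

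Two further limits are fair. Section 5.3 does not mention bleeding; 5.6 and 3.2 do. The link between switching and blood loss is thus a reasonable inference rather than a stated trigger, and the explicit route to losing patients is 5.6, which covers both arms. Also, a reader might infer from the worst-case row that the effect would be halved or lost. That requires a CV of 0.5 or more and three switchers who are exactly the three heaviest bleeders. It also holds for means only, while 9.4 turns to the Mann-Whitney test for non-normal variables, and the medians move less.

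**Conclusion.** The defect is an inconsistent definition of the comparison groups together with the absence of any stated analysis population. The handling of patients switched under 5.3 or removed under 5.6 is left open, and one available reading gives a non-randomized comparison on the primary endpoint. It should be corrected before analysis.

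The size cannot be established from the documents. Under the assumptions above, one high-loss control lost moves a true ratio of 0.80 to about 0.81 to 0.90. The three highest lost, as an upper bound, move it to about 0.85 at the CV implied by 60 patients and to 0.90 to 1.05 at CV 0.5 to 1.0. All of these run against the device, so they do not support an inference that the wording would create a false benefit. That direction belongs to the drop-out reading alone. Counting converted high-loss Thunderbeat patients as comparators too would raise the comparator mean and push the other way, and removals under 5.6 could fall in either arm.

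**What to change.** Reword 9.4 along these lines: *Patients randomized to Thunderbeat will be compared with patients randomized to the conventional group, whatever techniques were used during surgery.* Then:

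- Apply the same grouping to the regression models, and align the comparator wording in 2.1 and 2.2 with assignment.
- State that patients switched under 5.3 or removed under 5.6 stay in the analysis in their assigned arm, using blood loss and 90-day data already collected in routine care, subject to consent. Say the same for any randomized patient who meets the second exclusion criterion of 3.2 at dissection.
- Report the number of switches and removals, with reasons, by arm.
- Label any comparison by technique used as a sensitivity analysis.

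The cost is a few sentences. Section 5.2 already has the assignment recorded in the case report file, blood loss comes from the anesthesia notes (5.3), and the 90-day status is a record review without patient contact (Appendix B). The sample size does not change, and the surgeon's clinical freedom under 5.3 and 5.6 is untouched.

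### Section 9.4 states the Levene's-test condition the wrong way round, so evidence of unequal variances triggers the equal-variance t-test (minor; immaterial at 30 vs 30)

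*Combined protocol and SAP*

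**What the plan says.** Section 9.4 assigns "t-tests for continuous variables" and then sets the rule for choosing between the two versions of that test: "equal variances were not be assumed, unless significant by Levene"'s test. The default is thus unequal variances (Welch), and a significant Levene result is the stated exception. The significance level for Levene's test is not given.

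The same paragraph limits the rule's reach. Mann-Whitney "tests will be utilized for non-normally distributed variables", and two-tailed P "values 0.05 will be considered statistically significant". The regression models described next do not use the Levene step. The plan does not list which outcomes will be t-tested, so blood loss, the primary endpoint in section 9.1, may or may not come under the rule.

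On arm sizes, section 9.2 specifies "random block sizes in a 1:1 allocation ratio", and section 9.3 says "The total expected enrollment is 60 patients: 30 Thunderbeat and 30 conventional". Section 5.6 allows patients to be removed from the study. It gives no expected rate and does not say whether they leave the analysis.

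**The concern.** Levene's null hypothesis is that the variances are equal, so a significant result counts against equality. The stated exception therefore runs backwards: the pooled test is reserved for the datasets in which its assumption has been rejected, and Welch is kept for those in which it has not.

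Two things are at stake. The first is type I error for any t-tested outcome whose spread differs between arms, because the pooled test is sensitive to unequal variances when the arms also differ in size. The second is whether the plan can be carried out as written. An analyst must either apply a backwards rule or depart from the plan without saying so.

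**Working it through.** **Inputs from the document.** 30 per arm, 1:1 (sections 5.2, 9.2, 9.3); two-sided 0.05 (section 9.4; section 9.3 has "alpha error set at 0.05, power>80 percent"); the Levene rule as quoted. Section 9.3 also gives an "assumption of difference of 20 percent in blood loss in favor of the Thunderbeat" device, but no SD or control mean. Its total of 60 therefore cannot be reproduced, and this point does not depend on it.

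**Assumptions.** Levene's test is mean-centred at 0.05, the data are normal, and SD ratios run from 1.25 to 3. A ratio of 1.25 is what a 20% proportional reduction implies if the coefficient of variation is constant (1/0.80 = 1.25), which is itself an assumption. The other ratios and all unequal splits are illustrations.

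**Step 1: equal arms, by formula.** With n = 30 in each arm, the pooled and Welch standard errors both equal √[(s₁² + s₂²)/30], so the two t statistics are identical. Only the degrees of freedom differ. Pooled df = 58. For SD ratio r, Welch df = 29(1 + r²)²/(1 + r⁴). For r = 2 this is 29 × 25/17 = 42.6.

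| SD ratio | Welch df | Welch critical value (pooled: 2.002) | Welch p when pooled p = 0.0500 |
|---|---|---|---|
| 1.5 | 50.5 | 2.008 | 0.0507 |
| 2 | 42.6 | 2.017 | 0.0517 |
| 3 | 35.4 | 2.029 | 0.0530 |
| limit | 29 | 2.045 | 0.0547 |

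At 30 vs 30, choosing the wrong version can move a borderline p-value from 0.050 to no more than 0.0547.

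**Step 2: equal arms, by simulation.** 400,000 null trials per scenario (Monte Carlo SE about 0.03 points). As written means pooled if Levene is significant, otherwise Welch.

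| SD ratio | As written | Always Welch | Verdicts differ |
|---|---|---|---|
| 1.25 | 5.04% | 5.02% | 0.02% |
| 1.5 | 4.99% | 4.93% | 0.06% |
| 2 | 5.16% | 5.00% | 0.16% |
| 3 | 5.26% | 4.98% | 0.28% |

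The branch is reached often: Levene is significant in about 51% of trials at ratio 1.5 and 92% at ratio 2. It simply has little effect when the arms are equal. In a separate run of 100,000 trials per scenario, at an effect giving about 79% power, the stated rule and its reverse differ by at most 0.8 points (78.69% vs 77.87% at ratio 3). With lognormal data their type I errors differ by at most about 0.1 point.

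**Step 3: unequal arms (assumed 30 vs 24).** Each cell gives type I error with the smaller arm more variable, then with the larger arm more variable. Reversed means Welch if Levene is significant, otherwise pooled.

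| SD ratio | As written | Condition reversed | Always Welch |
|---|---|---|---|
| 1.25 | 5.25% / 4.82% | 5.43% / 4.68% | 5.03% / 5.00% |
| 1.5 | 5.70% / 4.53% | 5.51% / 4.66% | 5.05% / 5.01% |
| 2 | 6.75% / 3.91% | 5.23% / 4.91% | 5.04% / 5.03% |

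The effect shrinks with milder imbalance. At 30 vs 28, smaller arm more variable, ratio 2, the three rules give 5.7%, 5.1% and 5.1%. It grows with greater imbalance: at 30 vs 20 under the same conditions they give 8.0%, 5.5% and 5.0%.

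**The case against.** The strongest reply is that this is a copy-edit. The sentence is visibly garbled, it starts from the robust default, and the author may well have meant that equality would be assumed only if Levene's test supported it. Under the planned design nothing of consequence follows. The larger figures need a one-sided loss of patients that no section predicts: section 9.4 compares patients as assigned, blood loss and operating time are recorded on the day of surgery, and section 5.6 does not say that removed patients leave the analysis. The scope is also narrow, since non-normal variables go to Mann-Whitney and section 9.4 describes the analysis as descriptive.

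Most of this stands as an argument about weight. The inversion itself, compared with the reversed condition, costs only about 0.2 points at 30 vs 24 and ratio 1.5 (5.70% vs 5.51%). At ratio 1.25 the current text is slightly closer to 5% than the reversed one. Half of the unequal-arm cases are conservative.

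What it does not do is make the stated rule correct. The garbling affects the verb, while the condition is clear and has one literal reading. The likely intention cannot be shown from the document.

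It can also be said that reversing the condition would cure the slip without moving to Welch throughout. That would correct the logic, but it keeps a preliminary test that protects type I error less well than Welch alone.

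**Conclusion.** The concern holds as a minor error. Section 9.4 states the Levene condition backwards and no other section corrects it. At 30 vs 30 there is no material effect: type I error stays between 5.0% and 5.3% for SD ratios of 1.25 to 3, and at most 0.28% of null trials change verdict. A noticeable effect needs both unequal analysed arms and SDs differing by about 1.5-fold or more. In the 30 vs 24 illustration, type I error is then 5.7% or 4.5% at ratio 1.5, and 6.8% or 3.9% at ratio 2, against about 5.0% for Welch.

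These sizes rest on normal data, a Levene level of 0.05, and assumed SD ratios and arm sizes. The point applies only to outcomes that are t-tested. It does not show that the primary blood-loss result would change.

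**What to change.** Replace the Levene sentence in section 9.4 with: *Equal variances will not be assumed; the Welch t-test will be used for all t-test comparisons.* In the sentence before it, change Student's to Welch so that the two agree.

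This keeps the plan's own default and removes the preliminary test. Merely reversing the condition is the weaker option: at 30 vs 24 it is no better than the current text at SD ratio 1.25, barely better at 1.5, and clearly better only at about 2.

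The cost is two adjacent sentences. Data collection and sample size are unaffected.
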